All encounters will take place in private rooms, via the online platform, via email communication, via secure text messaging, or through a secure phone call. We will offer patients the option of having the survey completed without any other people present in their room or they can complete it on their own time. Patients have the option of the research assistants assisting them in completing the survey or filling out the survey by themselves. Patients who choose to share their Facebook, Twitter, Instagram or other digital data will be given a unique ID that will be linked to identifiable information. Participants who install the application to share their Facebook posts will be able to opt in and out of the application at their discretion. Patients will be asked by a RA if they would be willing to anonymously share their Facebook/Instagram posts for health research (Example description: "Penn researchers are trying to learn if certain language is associated with certain health outcomes. Would you be willing to share your Facebook posts with researchers? Your posts will be anonymous -- that is, not connected to your name -- and you can choose to stop sharing your posts at any time.") The Facebook/Instagram application will access data that is stored in the user profiles in the Facebook/Instagram platform. When participants first click on the link to use the app, they will first be greeted by the Facebook/Instagram consent screen that will ask the user permission for the application to have access to their profile information and to consent to the terms and service of the application. Participants would have to agree to this screen in order to use the application. They will have to click agree to access the application (at least at the first time). All language data will be stored on a secure server using only the unique study ID which can be used to link this data to Center for Digital Health data collection platform, (<https://donate.centerfordigitalhealth.upenn.edu/capture/>). This linkage will be stored in a double locked fashion on a password protected computer and will be accessed only by the principal investigator and key study personnel. For the participants who select to enroll in an interview, interview audio-recordings will be transcribed verbatim, and all identifiers will be removed. Transcripts and audio files will be saved on a Penn Medicine managed, HIPAA compliant server. Interview audio-recordings will be transcribed verbatim and all identifiers will be removed. The recording and transcript will be kept in a secure and locked area with access limited to designated researchers. After we analyze the recordings, we will destroy recordings after data analysis or completion of the study. All encounters will take place on Penn Medicine Zoom videoconference. When utilizing Zoom for audio recordings, additional steps will be made by the research team to ensure participant safety. Based on guidelines, researchers will ensure the following settings for privacy and compliance for Penn Zoom. 1) Researchers will turn off the Personal Meeting ID setting and instead opt for the meeting ID to be generated automatically, allowing for new

links and meeting IDs to be created for each meeting. 2) Research staff will turn off Cloud Recordings and ensure only local recordings that are HIPAA compliant are used as they are encrypted and managed by PMACS/DART or UPHS. The recording and transcript will be kept a secure and locked area with access limited to designated researchers. After we analyze the recordings, we will destroy recordings after data analysis or completion of the study. All survey data will be stored in a secure, web-based database (Way to Health or REDCap) where a study ID number will be generated for each patient. A link between the study ID number and the patient PHI will need to be maintained to ensure that the study staff can track recruitment efforts to potential participants and to avoid contacting any patients who have previously declined to participate. To ensure that patient confidentiality is preserved, individual identifiers (such as name) are stored in a single password protected system that is accessible to study research, analysis and IT staff only. This system is hosted on site at UPenn and is protected by a secure firewall. Once a participant is in this system, they will be given a unique study ID number. Any datasets and computer files that leave the firewall will be stripped of all identifiers besides the study ID and individuals will be referred to by their study ID only. The study ID will also be used on all analytical files. Way to Health and REDCap are secure web applications for building and managing online surveys and databases. Privacy of all study data will be maintained by restricting access to the identifiable information only to approved study staff who have received subject confidentiality and privacy training. Study coordinators will access patient contact information from the database to conduct recruitment phone calls. The study coordinator will review the consent script, which will include a description of the voluntary nature of participation, the study procedures, risks and potential benefits in detail. Participants will be told that all information will be kept strictly confidential, except as required by law. Subjects will be provided a copy of the consent document. All efforts will be made by study staff to ensure subject privacy. This database is hosted on a secure server as detailed in the subject confidentiality section.

Disclosures

Will any data or specimens from Penn participants OR other research generated work product (e.g., intellectual property) be disclosed to any individuals, entities, or vendors, etc. outside of Penn?

No

Data Protection*

- Name**
- Street address, city, county, precinct, zip code, and equivalent geocodes**
 - All elements of dates (except year) for dates directly related to an individual and all ages over 89**
- Telephone and fax number**
- Electronic mail addresses**
- Social security numbers**
- Medical record numbers**
- Health plan ID numbers**
 - Account numbers**
 - Certificate/license numbers**
 - Vehicle identifiers and serial numbers, including license plate numbers**
 - Device identifiers/serial numbers**
- Web addresses (URLs)**
- Internet IP addresses**
 - Biometric identifiers, incl. finger and voice prints**
 - Full face photographic images and any comparable images**
 - Any other unique identifying number, characteristic, or code**
- None**

Does your research request both a waiver of HIPAA authorization for collection of patient information and involve providing Protected Health Information ("PHI") that is classified as a "limited data set"

(city/town/state/zip code, dates except year, ages less than 90 or aggregate report for over 90) to a recipient outside of the University of Pennsylvania covered entity?

No

Tissue Specimens Obtained as Part of Research*

Are Tissue Specimens being obtained for research?

No

Tissue Specimens - Collected during regular care*

Will tissue specimens be collected during regular clinical care (for treatment or diagnosis)?

No

Tissue Specimens - otherwise discarded*

Would specimens otherwise be discarded?

No

Tissue Specimens - publicly available*

Will tissue specimens be publicly available?

No

Tissue Specimens - Collected as part of research protocol*

Will tissue specimens be collected as part of the research protocol?

No

Tissue Specimens - Banking of blood, tissue etc. for future use*

Does research involve banking of blood, tissue, etc. for future use?

No

Genetic testing

If genetic testing is involved, describe the nature of the tests, including if the testing is predictive or exploratory in nature. If predictive, please describe plan for disclosing results to subjects and provision of genetic counseling. Describe how subject confidentiality will be protected Note: If no genetic testing is to be obtained, write: "Not applicable."

Not applicable

Consent

1. Consent Process

Overview

We will enroll patients in person and remotely. For in-person enrollment, we will meet patients during their in-patient stays at HUP, PAH, or PPMC or an outpatient primary care visit at Penn Medicine who are between the ages of 30-74. For remote enrollment, we will call/email/text message potentially eligible patients. Potentially eligible patients will be approached or called/mailed/text messaged to verify they meet all inclusion criteria and will then be asked to participate. An AA or CDH RA will first ask participants if they use Social Media, have a Gmail account, and what type of step data. For those who do not use any, the encounter ends as these patients are not eligible. Patients who are potentially eligible, they will be told that they may be eligible for a research study looking at digital data and coronary heart disease (CHD). Subjects will be asked to confirm whether they will share their digital data with health researchers as described in this protocol. The language will be similar to (but not verbatim): "Penn researchers are trying to learn if digital data is associated with cardiovascular health. Would you be willing to share your Facebook posts with researchers? Your posts will be anonymous -- that is, not connected to your name -- and you can choose to stop sharing your posts at any time." The RA will obtain informed consent using the attached consent form via a HIPAA-compliant online survey/data collection platform (<https://donate.centerfordigitalhealth.upenn.edu/capture/>), or REDcap. The participants will sign an electronic version of the consent form (stored on the Center for Digital Health data collection platform, (<https://donate.centerfordigitalhealth.upenn.edu/capture/>) or REDcap and will be either emailed a copy of their signed informed consent or handed a copy of the informed

consent for their records. The RA or AA will describe the study in detail, including the use of information from their medical record, the survey, the use of Google takeout, how their steps are calculated, and the use of the Facebook/Instagram app to extract their posts for language analysis and how Reddit and Twitter data is extracted. The participant may refuse to answer any questions for any reason, can skip any question, and can stop participation at any time. Subjects may contact the research team as described in the consent to have their information destroyed. The research presents no more than minimal risk of harm to subjects and involves no procedures for which written consent is normally required outside of the research context. All study activities are conducted either while the patient is in the hospital during this brief encounter, over the phone using a HIPAA secure telemedicine application (Doximity), via email using our Centers shared pennmedicine.upenn.edu email address, or via MPM or W2H. The research presents no more than minimal risk of harm to subjects and does not involve procedures for which written consent is normally required outside of the research context. The study is not intervening or currently changing patient care. Participants who complete the additional survey will complete a separate informed consent document on RedCap. All participants will have the option to complete the document with a research coordinator.

Children and Adolescents

N/A

Adult Subjects Not Competent to Give Consent

N/A

2. Waiver of Consent

Waiver or Alteration of Informed Consent*

No Waiver Requested

Minimal Risk*

Impact on Subject Rights and Welfare*

Waiver Essential to Research*

Additional Information to Subjects

Written Statement of Research*

No

If no written statement will be provided, please provide justification

The following documents are currently attached to this item:

There are no documents attached for this item.

Risk / Benefit

Potential Study Risks

The potential risks associated with participating in the study are minimal. Regarding unforeseen safety issues, the researchers will take every step to ensure these do not occur. Participants will have every opportunity to stop the survey at any time or discontinue participation.

Potential Study Benefits

There are no direct benefits to participation. Participants are contributing to health research in general by providing information which could improve ability to use language and social media data to predict certain health outcomes and health care utilization.

Alternatives to Participation (optional)

N/A

Data and Safety Monitoring

The principal investigator will be responsible for monitoring the data of the study. The safety, privacy, and data integrity will be maintained as described in the confidentiality section. The PI will ensure all researchers are adhering to the study protocol and applicable research regulations and Penn requirements. This includes weekly lab meetings and monthly discussions of data integrity and study progression. Interim analysis will be completed regularly for the duration of the study. All digital media data, focus group, and survey data will be collected and stored on servers that sit behind the health system firewall. Subject names and other relevant PHI will be removed if data are to be shared with auditors and other investigators for whom this information is not required. Consent materials and documentation will be kept as part of the secured study files. All study data will be carefully structured and maintained such that participants will be protected. Data will be kept in locked research offices and stored on the secure Penn server. Computer files containing data will be password-protected, and records will only be made available to research personnel who are IRB approved.

The following documents are currently attached to this item:

There are no documents attached for this item.

Risk / Benefit Assessment

Based on the potential risks and benefits described above, we believe this study may be considered minimal risk.

General Attachments

The following documents are currently attached to this item:

[Cover Letter \(letter.docx\)](#)

[Additional forms \(screenshot2025-08-01at1.42.438239pm.png\)](#)

## Final Analysis Plan

As digital data exist in multiple formats (e.g. posts, photos, searches, steps) we will analyze each source according to its specific attributes. We will systematically apply robust data-driven approaches to parsing and stratifying data. This step requires significant data pre-processing and annotation as raw digital data is not directly interpretable. This will also occur over multiple iterations over the course of the grant as new terms (e.g., the term "vaping" describes use of e-cigarettes) and digital sources emerge. To automatically extract meaningful variables from the text, we will use both dictionary-based (e.g., counting words from previously constructed word lists, lexica) and data-driven "open vocabulary" methods which automatically generate lexica and identify important words and phrases based on the data itself rather than *a priori* categories. For dictionary analyses, we will use the Consumer Health Vocabulary, an online open source thesaurus of colloquial and technical medical terms and the Unified Medical Language System which contains lists of medical terms and vocabulary to identify disease discussions. We will specifically focus on words and words associated with previously identified predictors of CHD (e.g. demographics, family history, lifestyle, comorbidities, blood pressure) as identified in a systematic review of prediction models for cardiovascular risk by Damen et al. BMJ 2016. We will create classifiers to determine if a given instance of a disease term is referring to the disease or something unrelated (e.g. "If I see a celebrity I will have a heart attack" vs. "I am having chest pain, SOB and had a prior heart attack"). Our prior work has demonstrated that, as one might guess, some CV diseases, like "hypertension", are almost always used in their medical context while others, like "heart attack", are often used colloquially. We will also create classifiers to categorize language by broad grouping such as risk factors, treatment, medication adherence, symptoms, and by more granular categories such as active/sedentary, healthy food/unhealthy food, smoking. We will compare the performance of several machine-learning algorithms (e.g. support vector machines, random forests, and, in cases with adequate data, deep learning) and assess the accuracy of our disease term classifier against hand-annotated data. For multiword phrases we will use approaches for determining the probability that words occur together (e.g., pointwise mutual information PMI). We will also use additional linguistic models to account for more subtle language complexities and nuance such as parts of speech, and disambiguated words. We will use automated computational methods (e.g., deep learning-based object recognition) combined with manual coding to classify features (e.g., healthy or unhealthy food, physical activity, smoking, and drinking) in images. To determine nutritional content of food images, for example, we will use the imagga.com image classification software, combined with analysis of the words used in the text associated with images to recognize

food images. Those images that are food images will then, to the best of our ability, be compared to a list of healthy and unhealthy

groupings (e.g. high salt, high fat) and also compared to a USDA database of precise nutritional values for over 30 nutrients for 8600 food items. We will also construct a convolutional neural network based on labeled food and health behavior-related images to train a model to recognize images in the most frequent categories which our first pass fails to find. We will analyze the labeled images to better understand the nature of food posting, and how they vary with the time of day, demographics of the person posting the image. We will compare summary data from smartphones with self-reported data. Time series data from sensors will be used to analyze presumed changes in behavior using a previously validated health behavior activity change detection framework which segments time series data by time periods, identifies changes and their significance, and identifies the presumed locus of changes. The strength of using different types of data (text, images, sensors) is that each provides a unique type of information. Sensors provide direct measurements of protective and risk factors for CV, but they only measure what they are intended to measure. On the other hand, text and image data have been shown to capture a wide variety of information about people from demographics and personality to mood and beliefs. Further, each patient may use differing proportions of each modality such that, for example, text may make up for a lack of images and vice-versa. As digital media data may over-represent, under-represent or not represent health behaviors we will compare survey data and clinical data with digital data to quantify differences in behaviors and risk factors. We will explore statistical and machine learning methods for combining heterogeneous variables into predictive models. For our main analysis, we will both explore the correlations between the different modalities to better understand when they provide redundant or non-redundant information and we will, more importantly, combine the different modalities into a single predictive model. Standard machine learning methods such as random forests make it easy to add heterogeneous features to a single predictive model, and give measures of variable significance indicating how much each feature contributes to predictive accuracy. We will also test more sophisticated machine learning methods for combining multiple modalities in a single model, such as using extensions of the 'elastic net' regression and dimensionality reduction framework that account for the fact that different modalities require different regularization penalties. We will also explore imputation and "back-off" methods that account for the fact that different patients will have substantially different amounts of data available in different modalities. These methods work by either estimating ("imputing") values for the missing data or automatically adjusting the weights given to different modalities for each patient based on the amount of data available for that patient. For Objective 1: Sample characterization: We will use

summary statistics to describe patient demographics, survey response data, and digital data usage (e.g. frequency of posting, number of social media platforms). Descriptive data will be presented as mean (SD) for continuous variables and frequencies of participants for categorical variables. 5b Extracting topics and features: We will use the Mallet package for implementation of the Latent Dirichlet Allocation (LDA) method for clustering language data of all participants. The LDA probabilistic model assumes that documents (e.g. Facebook status updates) contain a distribution of topics which then contain a distribution of words. Ultimately, words are grouped together by considering the other words they appear with. Descriptive statistics, t-tests (continuous measures) and chi-squared tests (categorical measures) will be used to compare topics and features with survey data. For example, NHANES survey questions (e.g. Do you now smoke cigarettes?) would be compared with images of cigarette smoking. For Objective 2: We will compare prediction models with and without digital variables. Probability weighted Cox proportional hazard analysis with robust variance estimates will be used to assess the association between each variable from digital media and CHD in univariable and multivariable models. We will use graphical and analytical methods to test the proportional hazards assumption for each analysis. To evaluate the predictive strength of digital data, we will build four predictive machine learning models using a stepwise sequence to select the most parsimonious model using combinations of risk factors. (1. Framingham predictors / American College of Cardiology ASCVD Risk Estimator Plus alone, 2. Framingham predictors / American College of Cardiology ASCVD Risk Estimator Plus + SES, 3. Framingham predictors / American College of Cardiology ASCVD Risk Estimator Plus + digital topics/ features, 4. Framingham predictors / American College of Cardiology ASCVD Risk Estimator Plus + digital topics/features+ SES) For Objective 3: We will use Super Learner, the ensemble machine learning approach which allows for the specification of multiple plausible candidate prediction models. Each of the candidate models is applied to a training set and outcomes are predicted using the validation set. A loss function is calculated within each validation set and then averaged across validation sets, which provides the estimated cross-validated risk score for each method. Calibration will be assessed using a calibration plot comparing the predicted probabilities (obtained using fixed regression coefficients of the prediction models) with the observed probabilities. The Super Learner algorithm finds the optimal weighted combination across all of the specified methods. Van der Laan et al. proved the asymptotic efficiency of the Super Learner algorithm and demonstrated that the optimal combination performs at least as well as the best estimators from the candidate models. We will implement Super Learner in R (The R Foundation for Statistical Computing). In this approach generalized estimating equation (GEE) and generalized linear mixed effects models will be explored to account for repeated measures per patient over time. One of the challenges of cost analyses is censoring, since cost may be incomplete and available for

some patients and not others. As the dependent variable will be cost, we will be attentive to informative censoring and right skewness, potentially using generalized linear models under a gamma distribution and log link. To account for informative censoring we will use inverse probability of censoring weighting. We will also explore the application of our new nested g-computation approach that allows for informative censoring and time- varying covariates to obtain future cost predictions. Additionally, we will generate summary statistics to describe the cohort and survey responses. We will use the model-based approach of latent class analysis (LCA)- to classify individuals into previously unmeasured subgroups. Variables to include in the LCA will include: demographics, years of platform use, posting: volume, quality, retransmission, and engagement. We will use the Bayesian information criterion to assess goodness of model fit, entropy to assess variations between classes, and the parametric bootstrapped likelihood ratio test to assess if a model with  $k$  classes has better performance than  $k-1$  classes. We will then use a regression model to compare with measures of health status, social media perceptions, and readiness/activation for each latent class. Models will be adjusted for demographics.

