The primary outcome variable for the first objective will be topics and features (derived using the Latent Dirichlet Allocation [LDA] method for clustering language data) as well as a model-based approach of latent class analysis (LCA). We hypothesize: H1: There will be a difference in themes and topics posted by patients with heart disease and for patients without heart disease and use and engagement

phenotypes reflecting quantity, quality, and interaction of posts will be associated with health status, social media perceptions, and patient activation. The second objective outcome variable will be any CHD event. We hypothesize: H2: Adding digital data variables to conventionally-derived predictive models will improve the AUC for forecasting/predicting a CHD related event in a patient. The third objective outcome measure will be health care utilization measured by cost. We hypothesize: H3: Unique digital data variables identified for patients with heart disease and without heart disease will better predict future health care utilization costs for the health system. The fourth objective outcome measure will be the impact of dynamic health events on CV health behaviors. We have the following three hypotheses: H4,1: Digital media data will provide valid measures of health behaviors when compared with traditional sources. H4,2: Variations in digital data about modifiable CV health behaviors will correlate with dynamic health events. H4,3: Modifiable CV health behaviors (smoking, poor diet, and reduced physical activity) will increase more in response to dynamic health events in low income and minority communities.

Secondary outcome variable(s)

Given the correlational nature of this research the distinction between primary and secondary outcome variables is not particularly apparent.

Background

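### The heart-disease topic contrast in H1 is assigned no test, single-feature tests have no error-control rule, and chi-squared cannot measure over- or under-representation

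*SAP*

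**What the plan says.** **Hypothesis.** In the Protocol, Primary outcome variable(s), the topic half of H1 reads: "There will be a difference in themes and topics posted by patients with heart disease and for patients without heart disease". The other half concerns use and engagement phenotypes. Overall objectives words Objective 1 as finding topics and features associated with CHD and its risk factors.

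**Objective 1 analysis.** The SAP (Final Analysis Plan, Objective 1) fits LDA to the language of all participants. Then: "Descriptive statistics, t-tests (continuous measures) and chi-squared tests (categorical measures) will be used to compare topics and features with survey data". Its example sets a survey smoking item against images of smoking.

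**Nearest disease analysis.** Under Objective 2, a probability-weighted Cox model is to "assess the association between each variable from digital media and CHD in univariable and multivariable models". The Protocol says of that objective: "The second objective outcome variable will be any CHD event".

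**Phenotype half.** The latent-class regression at the end of the SAP covers it: "Models will be adjusted for demographics". The demographics are not named.

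**Features.** Open-vocabulary methods are to "automatically generate lexica and identify important words and phrases based on the data itself", over several iterations during the grant. The number of topics is not given. Data and Safety Monitoring in the Protocol adds regular interim analysis.

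**Priority and aim.** For the main analysis the SAP will explore correlations between data types and, "more importantly, combine the different modalities into a single predictive model". It compares survey and clinical data with digital data for this reason: "As digital media data may over-represent, under-represent or not represent health behaviors".

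**The concern.** There are three linked gaps.

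- **No test is assigned to H1's topic contrast.** The Objective 1 tests have survey answers, not heart-disease status, on the other side. The contrast, the model and the covariates could therefore be chosen after the data are seen.
- **Single-feature tests have no error control.** Neither document states a significance level, a multiplicity rule or an exploratory label for them. With features generated and regenerated from the data and looked at repeatedly, the list of topics declared different could contain an unknown share of false ones.
- **The named test does not match the aim.** Over- or under-representation is a signed difference between two measures in the same people. A chi-squared test of one against the other asks only whether they are associated.

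**Working it through.** The plan gives no error rate, power or effect size for these tests, so there is no stated figure to reproduce. The only input taken from the documents is N = 1000 (Protocol, Study duration). Everything else below is an assumption.

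**1. Which analysis answers which claim**

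| Claim or aim | Analysis named for it |
|---|---|
| H1, topics by heart-disease status | none assigned; the Objective 1 tests are against survey data |
| H1, phenotypes | latent-class regression, adjusted for unnamed demographics |
| Objective 2, any CHD event | Cox model per digital variable (no covariates listed); four prediction models with Framingham/ASCVD and SES sets |
| Size of digital-versus-survey differences | descriptive statistics, t-test, chi-squared; no paired difference, agreement measure or interval |

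**2. False share of declared topics without control**

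Assume each topic is tested two-sided at 5%, a proportion π of topics truly differ, and each true difference is d = 0.2.

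- Shift = d × √(n1·n2/(n1+n2)). At 500 vs 500 this is 0.2 × √250 = 3.162, giving power of 0.885.
- False share = 0.05(1−π) / [0.05(1−π) + power × π].
- At π = 2%: 0.0490 / (0.0490 + 0.0177) = 73%.
- At π = 50%: 0.025 / (0.025 + 0.4427) = 5.3%.

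| Groups | Power | π = 2% | 5% | 10% | 25% | 50% |
|---|---|---|---|---|---|---|
| 500 vs 500 | 88.5% | 73.5% | 51.8% | 33.7% | 14.5% | 5.3% |
| 200 vs 800 | 71.6% | 77.4% | 57.0% | 38.6% | 17.3% | 6.5% |
| 200 vs 200 | 51.6% | 82.6% | 64.8% | 46.6% | 22.5% | 8.8% |

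The 200 vs 200 row represents 400 people supplying text. It is relevant because Key inclusion criteria require an account on only one platform or device. At d = 0.3 and 500 vs 500 the share runs from 71.1% to 4.8%. The share does not depend on the number of topics.

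**3. With Benjamini-Hochberg at 5%**

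Simulated z-tests, 200 topics, d = 0.2, 4000 runs, for π = 2 / 10 / 50%:

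| Groups | False share | Power per true topic |
|---|---|---|
| 500 vs 500 | 5.0 / 4.6 / 2.5% | 38 / 58 / 80% |
| 200 vs 800 | 4.8 / 4.5 / 2.5% | 15 / 26 / 52% |
| 200 vs 200 | 5.0 / 4.1 / 2.5% | 6 / 8 / 23% |

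At 500 vs 500, correlating topics at 0.5 in blocks of 10 left the controlled share at 4.7 / 4.5 / 2.5%.

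**4. Chi-squared against under-representation**

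Assume 1000 people, of whom 15% report smoking. The cells are: both yes (a), survey only (b), image only (c), neither (d).

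- *Images flag 20% of smokers and 5% of non-smokers:* 30 / 120 / 42.5 / 807.5. Difference (c−b)/n = (42.5−120)/1000 = −7.75 points. SE = √[(b+c)/n − diff²]/√n = 1.25 points, so the 95% CI is −10.2 to −5.3. Chi-squared = 42.7. Observed agreement is 0.8375 and chance agreement 0.7993, so kappa = 0.0382/0.2007 = 0.19. Positive agreement 2a/(2a+b+c) = 0.27; negative agreement 2d/(2d+b+c) = 0.91.
- *Images flag 40% and 1%:* 60 / 90 / 8.5 / 841.5. Difference = −8.15 points. Chi-squared = 303.9. Kappa = 0.50.

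Under-representation is almost the same, yet chi-squared differs about sevenfold (303.9/42.7 = 7.1). Direction is lost too. With 20% survey smokers, perfect agreement (difference 0) and complete reversal (digital 80%, difference +60 points) both give chi-squared = 1000.

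**The case against.** **Objective 2 partly fills the gap.** Objective 1 is worded as topics associated with CHD, and the Cox analysis relates every digital variable to CHD. This stands in part. A reader might infer that no analysis links digital variables to heart disease, and that would be wrong. What is missing is the link: the Cox model belongs to an event outcome, does not compare topics between two patient groups, and lists no covariates. Because diagnosis outside UPHS is self-reported, some of the contrast might be read into the survey comparison, but the text does not say so.

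**The work is correlational, and prediction is the main analysis.** The Protocol does call the research correlational, and the SAP gives the combined model precedence. So the stronger inference, that missing multiplicity control undermines the prediction results, is not supported. But H1 is stated as a hypothesis, and no single-feature test is labelled exploratory.

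**Descriptive statistics can show two prevalences side by side.** True, so one cannot say that the plan rules out quantifying under-representation. It names no paired difference, agreement measure or interval. Chi-squared remains valid for asking whether a feature carries any signal.

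**The false shares rest on an assumed 5% level and an assumed contrast.** Correct. They describe uncorrected testing in general and are not an error rate measured in this trial.

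**Conclusion.** The concern holds in this limited form and should be addressed. The topic half of H1 has no analysis assigned to it, and single-feature tests have no error-control rule. The chi-squared test named for the survey comparison gives neither the size nor the direction of over- or under-representation.

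What is at risk is the list of topics reported as different and the digital-versus-survey comparison, not the combined prediction model. Under 5% testing with d = 0.2, the false share of that list is 5% to 73% at 500 vs 500 and 9% to 83% at 200 vs 200 as π falls from 50% to 2%. The spread is wide because π is unknown in advance, so neither end should be quoted alone. The reading of the text needs none of these assumptions.

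**What to change.** 1. **H1 topic half.** Assign a regression of each topic or feature on heart-disease status, adjusted for age, sex and any further demographics by name. State whether that status is the full code set I63 and I20-I25, which the Protocol (Design; Target population) labels CVD, or CHD only. List the covariates of the multivariable Cox models.
2. **Error control.** Apply Benjamini-Hochberg at 5% within each of three families: H1 topics and features; topics and features tested against survey items; Objective 2 univariable associations. Apply it once, to the feature set fixed at the final analysis, and label earlier looks exploratory. State the number of tests per family, and give effect sizes with intervals for every feature tested, declared or not.
3. **Digital measures with a survey counterpart.** Make the paired prevalence difference with its confidence interval the main measure, supported by kappa and positive and negative agreement. For continuous measures on the same scale, use the mean difference with limits of agreement. Include only participants who supplied that data type, and describe the result as agreement with self-report.

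**Cost.** SAP wording and no new data type, but the team should confirm that sex is recorded for patients outside UPHS, where there is no EHR access. Fewer topics will be declared. With 200 topics at d = 0.2, power per true topic falls from 88.5% to about 38-80% at 500 vs 500 and from 72% to about 15-52% at 200 vs 800, for π from 2% to 50%. At 200 vs 200 it falls from 52% to about 6-23%, which is why intervals for every feature matter.
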